Primary Study Endpoint	Completion of all provided questionnaires that capture subjectively reported headpiece retention and comfort, as compared to baseline.
Primary Safety Endpoint	Cumulative frequency of adverse events and events per participant
Safety Parameters	Rate of adverse events
Control	Each participant will act as their own control
Research Hypothesis	The investigational headpiece and compatible magnets will provide participants with a retention option that is acceptable for daily use.
Study Schedule	Consent: Participants or will sign an informed consent form prior to the conduct of any study procedures. Baseline: Participants will complete a questionnaire regarding experience with their own headpiece at the time of consenting and enrollment. Follow up: Participants will evaluate the investigational headpiece during a chronic period of up to one-year or until the investigational headpiece receives FDA approval. They will complete questionnaires at two-month intervals. Off-Study: Participants will return their investigational headpieces to the Sponsor.
Experimental Hypothesis	A significant portion of study participants will report that the investigational headpiece is acceptable for wear during daily life.

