3.3 Management and recruitment of study participants

Recruitment

- Participants who meet the study criteria will be recruited from cochlear implant recipient populations across North America. A participant's willingness and ability to meet the follow-up requirements will be determined and informed consent will be obtained. Participants under the age of 18, will be consented through a parent or guardian and provided a complementary assent, with age specific language for children ages 7-12 years and children ages 13-17 years. A signed and dated copy of this consent will be kept in the participant's study record and copy provided to the participant.

Participant Screening

- No investigational procedures are used to screen participants for study eligibility. Participants eligible to participate in this study will be evaluated according to the inclusion requirements for the study. Informed consent will be obtained before any study-specific tests or procedures are conducted. An individual is considered to be enrolled as a study participant only after the informed consent document has been signed and dated. Each participant will be assigned a unique identifier at the time of enrollment.

Inclusion criteria for participant selection

- Pre- or post-lingually deafened.
- Fluent in English, French, or Spanish or capable of communication with a caregiver who is providing consent.

Non-Significant Risk Study of a Cochlear Implant Headpiece

- Adult or child implanted with a commercially available Advanced Bionics cochlear implant. Children and adult participants are included to ensure device retention is appropriate for all implant populations.
- Have (or caregivers have) the cognitive and functional capability to comply with all directions during the study
- Be able to remove their own headpiece
- Have (or caregivers have) the cognitive and functional capability to complete the questionnaire required for the study
- Capable (or caregivers are capable) of reading and understanding patient information materials and giving written informed consent

Exclusion criteria for participant selection

- Have any significant medical condition that, in the opinion of any of the investigators, is likely to interfere with study procedures or likely to confound evaluation of study data.

Criteria and procedures for participant withdrawal or discontinuation

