- The present study is expected to continue at least for one year from initiation or until the investigational headpiece receives FDA approval, whichever comes last.

Expected duration of participation

- Duration of participation will vary from the time of enrollment to the one-year end point or until the investigational headpiece receives FDA approval, whichever comes last.

Number of participants required to be included in the clinical investigation

- A minimum of 20 participants will be enrolled in this present study, with a maximum of 200 participants.

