Following selection of the headpiece magnet and appropriate fit of the investigational headpiece, the study staff will introduce the Investigational Headpiece questionnaires that participants will complete at the initial visit and two-month intervals throughout their participation in the study. Participants will receive a number of questionnaires that would span the study duration. Pre-paid envelopes will be provided to allow participants to return completed questionnaires every two-months for the duration of the study.

At any time during the study, participants may request meetings with Investigators or Study Staff for changes in magnet strength or adjustments to the investigational headpiece, these meetings will be coordinated through a telephone call, email, or in-person conversation to set up additional visits.

Participants will return the investigational headpiece to the Sponsor at the end of this study. A pre-paid shipping envelope will be provided for this purpose.

Data collection and analysis of the present study will be administered from the Sponsor's location. Recruitment, participant consenting, and fitting of the investigational cochlear implant headpiece may be completed by study staff, with professional training with the Advanced Bionics cochlear implant system, at locations outside of the Sponsor's location. Investigators and study staff will complete training for this study that includes:

- Good Clinical Practice, including investigator responsibilities
- Informed consent procedures, including requirements for inclusion, exclusion, and all foreseeable risks
- Study protocol and procedures
- Processes for recording and reporting adverse events
- Device accountability procedures
- Data collection and correction procedures, source documentation, and record retention requirements

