11.0 Appendix 2 Questionnaires

	Non-Significant Risk Study of a Cochlear Implant Headpiece Investigational Headpiece Baseline Questionnaire	[REDACTED] [REDACTED] [REDACTED] [REDACTED]
---	--	--

Subject ID: [REDACTED] - [REDACTED] Subject # - Subject initials (First, Middle, Last; if no middle initial, use a "-")	Visit Date: [REDACTED] Month [REDACTED] Day [REDACTED] Year
---	---

If you have any questions during the evaluation, please consult with the [REDACTED]
[REDACTED] [REDACTED]

Please indicate your rating:

1. Rate the retention of your personal headpiece				
Very Acceptable	Acceptable	No Opinion	Unacceptable	Very Unacceptable
				

2. Rate the comfort of your personal headpiece				
Very Acceptable	Acceptable	No Opinion	Unacceptable	Very Unacceptable
				

Thank you for your participation.

Non-Significant Risk Study of a Cochlear Implant Headpiece

Non-Significant Risk Study of a Cochlear Implant
Headpiece
Investigational Headpiece Fitting Form

Subject ID: -
Subject # - Subject initials
(First, Middle, Last; if no middle initial, use a "-")

Visit Date: -
 Month Day Year

To be completed by Study Staff:

Right Side	N/A 	Headpiece SN:
------------	---------------------------------	---------------

Left Side	N/A 	Headpiece SN:
-----------	---------------------------------	---------------

Study Staff (Print Name)	
Signature:	
Date:	

Non-Significant Risk Study of a Cochlear Implant Headpiece

	Non-Significant Risk Study of a Cochlear Implant Headpiece Investigational Headpiece Questionnaire	[REDACTED]
---	---	------------

Subject ID: [REDACTED] - [REDACTED] Subject # - Subject initials (First, Middle, Last; if no middle initial, use a "-")	Visit Date: [REDACTED] [REDACTED] - [REDACTED] [REDACTED] Month Day Year
---	---

Please refer to the following instructions during your time wearing the new headpiece.

1. Provide feedback on the headpiece and magnet configurations when requested.
2. If any headpiece discomfort arises during the study, please discontinue use of the investigational headpiece and resume use of your personal headpiece.
3. Return all investigational products to the Advanced Bionics Study Staff after the evaluation.

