If you have any questions, please consult with the [REDACTED]

Date questionnaire was completed: [REDACTED]

[REDACTED]-[REDACTED]-[REDACTED][REDACTED]

Month Day Year

Please rate:

1. Is retention of the investigational headpiece acceptable?

Very Acceptable	Acceptable	No Opinion	Unacceptable	Very Unacceptable
				

2. Is comfort of the investigational headpiece acceptable?

Very Acceptable	Acceptable	No Opinion	Unacceptable	Very Unacceptable
				

Thank you for your participation.

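### The Fitting Form allows a headpiece on each side, but the visible rating items take one answer per participant, with no side field and no instruction for someone wearing two

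*Protocol*

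**What the plan says.** Eligibility (Protocol 3.3) covers "Adult or child implanted with a commercially available Advanced Bionics cochlear implant". Nothing there or in the synopsis excludes people with two implants, and the protocol does not mention bilateral users.

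The Fitting Form in Appendix 2 has separate right and left entries under one subject identifier. Each has its own N/A box and headpiece serial number, so staff can record a headpiece on the right, on the left, or on both.

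The rating forms in the same appendix are singular. The Baseline Questionnaire asks the participant to "Rate the retention of your personal headpiece" and has a matching comfort item. The follow-up form asks "Is retention of the investigational headpiece acceptable" and "Is comfort of the investigational headpiece acceptable". Each item has one row of five boxes. No visible field records a side or serial number, and nothing tells a participant with two headpieces how to answer.

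Protocol 3.4 says that "Participants will receive a number of questionnaires that would span the study duration". It does not say that one form is given per side, that only one side is fitted, or which side to rate.

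The synopsis states the experimental hypothesis per participant: "A significant portion of study participants will report that the investigational headpiece is acceptable for wear during daily life". The primary endpoint is "Completion of all provided questionnaires that capture subjectively reported headpiece retention and comfort, as compared to baseline".

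**The concern.** Section 2.0 explains that the tissue and hair between implant and headpiece vary, and that magnet strength is chosen to suit the individual. Retention and comfort can therefore plausibly differ between the two sides of one person. A bilateral user with one satisfactory and one unsatisfactory side cannot give a single answer that is true of both. That person has to pick the better side, pick the worse side, or average, and the form leaves the choice open.

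Two things are at stake. First, the participant-level share acceptable depends partly on an unrecorded choice by the respondent. Second, each participant is their own control, and the ratings are to be compared with baseline. A bilateral user fitted on one side only, or one who thinks of different ears on different occasions, may be comparing one ear's personal headpiece with the other ear's investigational one.

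An analysis plan not shown here cannot repair this, because side-specific answers are not requested on the visible forms.

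**Working it through.** The protocol gives no acceptability rate, bilateral share, power or alpha, so there is no figure of the plan's own to reproduce. The check has two parts.

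**1. The forms side by side**

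| Form (Appendix 2) | What it records per participant |
|---|---|
| Fitting Form | Right: N/A or serial number. Left: N/A or serial number |
| Baseline Questionnaire | One retention rating, one comfort rating, for the personal headpiece |
| Follow-up Questionnaire | One retention rating, one comfort rating, for the investigational headpiece |

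The Fitting Form can register two devices; the rating forms return one answer per item. No visible text links the two.

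**2. How far the answering choice could move the share acceptable (illustration)**

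Inputs, all assumed because the documents give none:
- q, the share of fitted sides that are not acceptable on a given item: 5% to 20%.
- b, the share of participants fitted on both sides: 10% to 50%.
- The two sides of one person are independent.
- Each rating is reduced to acceptable or not.

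Formulas:
- Every mixed user rates the better side: (1 − b)(1 − q) + b(1 − q²).
- Every mixed user rates the worse side: (1 − b)(1 − q) + b(1 − q)².
- The difference is 2bq(1 − q), which is also the share of participants with exactly one failing side.

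Worked case, q = 10% and b = 30%:
- Better side: 0.70 × 0.90 + 0.30 × 0.99 = 0.927.
- Worse side: 0.70 × 0.90 + 0.30 × 0.81 = 0.873.
- Difference: 2 × 0.30 × 0.10 × 0.90 = 0.054, or 5.4 points. The share of devices acceptable is 90.0% in both cases.

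Difference in percentage points over the range:

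| q | b = 10% | b = 30% | b = 50% |
|---|---|---|---|
| 5% | 0.95 | 2.85 | 4.75 |
| 10% | 1.8 | 5.4 | 9.0 |
| 20% | 3.2 | 9.6 | 16.0 |

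If the sides are correlated with coefficient ρ, the difference becomes 2bq(1 − q)(1 − ρ). At ρ = 0.5 every entry is halved; the worked case gives 2.7 points.

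**A count at the minimum sample size.** Section 3.3 says: "A minimum of 20 participants will be enrolled in this present study, with a maximum of 200 participants". Suppose that 6 of 20 participants are bilateral, 3 of those 6 have one failing side, and nothing else fails. There are 20 + 6 = 26 devices and 23/26 = 88.5% are acceptable. The reported participant share is 20/20 = 100% if the three rate the better side and 17/20 = 85% if they rate the worse side.

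**The case against.** The strongest case against is as follows.

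- **Two-sided fitting is inferred.** Right and left entries are also what a form needs to record which ear of a unilateral user was fitted, and section 3.4 speaks of the headpiece in the singular. This stands in part: the form permits two devices, but nothing shows how often two would be fitted.
- **The forms are partly hidden.** They are offered as examples, some header fields are redacted, and one form per side is not ruled out. So a side field cannot be fully excluded. The visible items and procedures show none.
- **A reader might infer that the outcome has no defined unit.** The documents do not support that. The hypothesis counts participants, and an overall personal judgement fits it. What is missing is narrower: a side field, and an instruction on how two sides become one answer.
- **A reader might infer that failing devices disappear and acceptability is inflated.** That is only one direction. A respondent who rates the worse side makes a good device look unacceptable. A failing side may also show up in adverse event reports or in visits for a magnet change, though not in the ratings.
- **A reader might infer that the primary endpoint is compromised.** As worded, that endpoint is completion of questionnaires. The share acceptable comes from the experimental hypothesis.
- **The figures are assumed and compare two extremes.** This stands. The protocol also states no acceptability threshold that a shift of this size could cross.

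**Conclusion.** The point holds as a gap in the data collection forms. The protocol's own Fitting Form allows two investigational headpieces on one participant, bilateral users are eligible, and the visible rating items cannot say which side an answer describes. For those participants the comparison with baseline may cross ears, and the share acceptable may be too high or too low.

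The size cannot be established from the documents. The illustrative range of about 1 to 16 points rests on independent sides, 5% to 20% of sides failing, 10% to 50% of participants bilateral, and all mixed users answering the same way. Correlated sides, or a mixture of answering habits, would make it smaller. With no bilateral participants the problem does not arise. The documents do not support a claim of systematic overstatement. The case for acting is that the change is cheap and the information cannot be obtained afterwards.

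**What to change.** On both the baseline and follow-up forms, give the retention and comfort items a Right and a Left answer row, each with an N/A box, matching the Fitting Form. Compare each side's follow-up rating with the same side's baseline rating. State in advance how two sides form one participant result. One option is to count a participant as acceptable only if every fitted side is rated acceptable; other rules are defensible, and the rule may sit in the analysis plan, provided it is fixed before the data are seen. If only one side per participant is meant to be fitted and rated, saying so and recording that side would also close the gap.

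The cost is one extra answer row per item on existing forms. Bilateral users tick four boxes instead of two. The share acceptable may be slightly lower: under the every-side rule, the worked case gives 87.3% of participants against 90.0% of devices.
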